## STUDY IDENTIFICATION

#### SYNOPSIS

**Title of study:** A Phase 1, Randomized, Double-blind, Placebo-controlled Study to Evaluate the Safety, Tolerability, and Pharmacokinetics of Single Ascending Doses of L606 for Inhalation in Healthy Subjects

#### **Objectives:**

The primary objective of the study is:

• To evaluate the safety and tolerability of single ascending doses of treprostinil after administration of L606 in healthy subjects.

The secondary objective of the study is:

• To assess the pharmacokinetic (PK) profile of single ascending doses of treprostinil after administration of L606 in healthy subjects.

#### Study design:

This will be a Phase 1, single-dose, randomized, double-blind, placebo-controlled, sequential-group study conducted at a single center.

Potential subjects will be screened (Days -28 to -2) to confirm that they fulfil the eligibility inclusion/exclusion criteria to enter the study. After verification of eligibility, subjects will be admitted to the Clinical Research Unit (CRU) on Day -1 (Check-in, the day before dosing). On Day 1, prior to dose administration, subjects will be randomized in a double-blinded fashion to L606 or placebo in a 6:2 randomization ratio.

The planned emitted dose escalation groups are:

- Group 1: 51 µg L606 or placebo volume equivalent to 51 µg
- Group 2: 102 µg L606 or placebo volume equivalent to 102 µg
- Group 3: 153 µg L606 or placebo volume equivalent to 153 µg
- Group 4: 204 µg L606 or placebo volume equivalent to 204 µg
- Group 5: 255 µg L606 or placebo volume equivalent to 255 µg
- Group 6: 306 µg L606 or placebo volume equivalent to 306 µg
- Group 7: 357 µg L606 or placebo volume equivalent to 357 µg
- Group 8: 408 µg L606 or placebo volume equivalent to 408 µg

L606 or placebo will be administered once in a solution for inhalation. The entire treatment procedure will be completed within 10 minutes.

On Day 3 (48 hours postdose), subjects will be discharged from the CRU after all protocol-specified assessments have been completed. Subjects will return for a Follow-up visit 7 to 10 days postdose. Based on the ongoing review of the safety, tolerability, and PK results, additional nonresidential visits may be required.

Safety and PK data will be reviewed following the completion of each group. Based on this data (as well as aggregate data from previous groups), a decision will be made to proceed with:

- 1) escalation to the next higher planned dose;
- 2) repeat evaluation of the same dose in an additional group;
- 3) evaluation of a lower intermediate dose before moving on to the next higher dose; or
- 4) discontinuation of dosing.

#### Number of subjects:

A total of approximately 64 subjects (8 subjects in each of 8 groups) will be enrolled in this study.

#### Diagnosis and main criteria for inclusion:

Healthy males and females 18 to 50 years of age, inclusive, with a body mass index between 18.5 and  $32.0 \text{ kg/m}^2$ , inclusive.

#### Investigational products, dose, and mode of administration:

Test product: L606 (liposomal treprostinil) solution, 1.5 mg treprostinil in 1.0 mL liposome solution Administration route: Oral inhalation completed within 10 minutes

#### Reference product and mode of administration:

Reference product: placebo solution (L606 solution excluding the active pharmaceutical ingredient [treprostinil])

Administration route: Oral inhalation completed within 10 minutes

#### **Duration of subject participation in the study:**

Planned Screening duration: Approximately 4 weeks

Planned in-residence duration: Approximately 4 days

Planned total study duration (Screening to Follow-up): Approximately 6 weeks

#### **Endpoints:**

#### Safety:

Safety will be evaluated by the incidence and severity of adverse events (AEs), incidence of serious AEs, the monitoring of vital sign assessments, 12-lead electrocardiograms, clinical laboratory evaluations, and physical examination.

#### **Pharmacokinetics:**

The plasma concentrations of treprostinil after L606 inhalation dosing will be determined using a validated bioanalytical method (liquid chromatography by tandem mass spectrometric analysis), and analyzed using noncompartmental method. The PK parameters will include area under the plasma concentration-time curve (AUC) from time zero to 2 hours postdose ( $AUC_{0-2hr}$ ), 4 hours postdose ( $AUC_{0-2hr}$ ), 8 hours postdose ( $AUC_{0-8hr}$ ), 12 hours postdose ( $AUC_{0-12hr}$ ), and 24 hours postdose ( $AUC_{0-24hr}$ ); AUC from time zero to the time of the last quantifiable concentration ( $AUC_{0-tlast}$ ); AUC from time zero to the time of the last quantifiable concentration ( $AUC_{0-tlast}$ ); AUC from time zero to infinity ( $AUC_{0-\infty}$ ); maximum observed plasma concentration ( $C_{max}$ ); time of the maximum observed plasma concentration ( $t_{max}$ ); apparent plasma terminal elimination half-life ( $t_{1/2}$ ); apparent total plasma clearance (CL/F); and apparent volume of distribution during terminal phase ( $V_z/F$ ). Other PK parameters may be calculated as appropriate.

#### Statistical methods:

#### Safety:

All safety data will be listed. Descriptive statistics and changes from baseline will be calculated for safety parameters as appropriate. These summaries will be produced for each dose level of L606 and the pooled placebo subjects. No formal statistical analyses are planned for the safety endpoints.

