### 3. INVESTIGATIONAL PLAN

#### 3.1. Overall Study Design and Plan

This will be a Phase 1, single-dose, randomized, double-blind, placebo-controlled, sequential-group study conducted at a single center. Overall, approximately 64 subjects are planned to be enrolled in 8 groups, with each group consisting of 8 subjects (Figure 2).

Potential subjects will be screened (Days -28 to -2) to confirm that they fulfil the eligibility inclusion/exclusion criteria to enter the study. After verification of eligibility, subjects will be admitted to the Clinical Research Unit (CRU) on Day -1 (Check-in; the day before dosing). Each subject will participate in 1 treatment period only and reside at the CRU from Day -1 to Day 3.

[figure not shown]
Sentinel dosing, where the first 2 subjects will be randomized 1:1 to L606 or placebo, will be used for the first 2 groups dosed. The remaining subjects in the group will be randomized 5:1 to L606 or placebo and administered study medication after the Investigator has reviewed the first 48 hours of safety data for the first 2 subjects. It is anticipated that any unanticipated safety and/or tolerability effects will be detected in the first 2 subjects dosed within a group. Sentinel dosing will not be required for subsequent groups.

All subjects will return for a Follow-up visit 7 to 10 days postdose.

Based on the ongoing review of the safety, tolerability, and PK results, additional nonresidential visits may be required. The number of additional visits per subject will not exceed 3 and will not extend beyond 28 days after dosing.

[figure not shown]
An overview of the study design is shown in Figure 1 and the planned dose levels are shown in Figure 2.

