### **3.4.** Discussion of Study Design, Including the Choice of Control Groups

A sequential-group, ascending-dose design has been chosen for safety reasons as this will be the L606 first-in-human study. Oral inhalation doses have been chosen for the study as this is the intended clinical route of administration.

Based upon the nonclinical data and clinical safety and efficacy information on the active ingredient, the duration of each treatment period is considered adequate to achieve the study objectives.

This study will be double-blind and placebo-controlled in order to avoid bias in the collection and evaluation of data during its conduct. Placebo has been chosen as the control treatment to assess whether any observed effects are treatment-related or simply reflect the study conditions.

The L606 data, along with clinical experience with treprostinil, suggest that single doses of L606 are unlikely to result in significant adverse effects in healthy subjects. Conducting the study in healthy subjects mitigates the potential confounding effects of the disease state and concomitant medications.

Sentinel dosing will be used in this study. To minimize risk, there will be an interval of at least 48 hours for evaluation of safety after the first 2 subjects have been dosed (1 with L606 and 1 with placebo) in each of the first 2 groups.

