### 5.2. Study Treatment Administration

Each dose of L606 and placebo solution will be self-administered by the subject via oral inhalation. The entire treatment procedure will be completed within 10 minutes.

Subjects will be administered the IMP in numerical order while seated and may be semi-recumbent but will not be permitted to lie supine for 2 hours after dosing, except as necessitated by the occurrence of an AE(s) and/or study procedures.

The planned emitted dose escalation groups are:

- Cohort 1: 51 µg L606 or placebo volume equivalent to 51 µg
- Cohort 2: 102 μg L606 or placebo volume equivalent to 102 μg
- Cohort 3: 153 µg L606 or placebo volume equivalent to 153 µg
- Cohort 4: 204 µg L606 or placebo volume equivalent to 204 µg
- Cohort 5: 255 µg L606 or placebo volume equivalent to 255 µg
- Cohort 6: 306 µg L606 or placebo volume equivalent to 306 µg
- Cohort 7: 357  $\mu$ g L606 or placebo volume equivalent to 357  $\mu$ g
- Cohort 8: 408 µg L606 or placebo volume equivalent to 408 µg

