### 8.4. Safety Analysis

All safety data will be listed. Descriptive statistics and changes from baseline will be calculated for safety parameters as appropriate. These summaries will be produced for each dose level of

L606 and the pooled placebo subjects. No formal statistical analyses are planned for the safety endpoints. Each AE will be coded using the Medical Dictionary for Regulatory Activities.

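### Does pooling the volume-matched placebo subjects distort the safety comparison across L606 doses?

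*Protocol*

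**What the plan says.** The Synopsis (Statistical methods, Safety) sets the layout of the safety tables: "These summaries will be produced for each dose level of L606 and the pooled placebo subjects". Section 8.4 repeats it and adds the limit on its use: "L606 and the pooled placebo subjects. No formal statistical analyses are planned for the safety endpoints". Both places also say that all safety data will be listed.

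On size and allocation, the Synopsis states "A total of approximately 64 subjects (8 subjects in each of 8 groups) will be enrolled in this study", and that "subjects will be randomized in a double-blinded fashion to L606 or placebo in a 6:2 randomization ratio". In the first two groups a sentinel pair is randomized 1:1, after which "The remaining subjects in the group will be randomized 5:1 to L606 or placebo" (Section 3.1).

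On the placebo, the Synopsis (Reference product) and Section 5.1 define it as the L606 solution without treprostinil. Section 5.2 ties its volume to the group's dose, up to Cohort 8: "L606 or placebo volume equivalent to 408" µg. Section 3.4 gives its purpose: "Placebo has been chosen as the control treatment to assess whether any observed effects are treatment-related or simply reflect the study conditions".

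On decisions, Sections 3.6 and 8.5 have the review committee look at blinded data between groups. Nearly all the stopping criteria in Section 3.7 count affected subjects within a group.

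**The concern.** L606 has one concentration, 1.5 mg/mL, so a higher dose means more liquid inhaled. Among L606 subjects, dose and vehicle volume are perfectly correlated, and only placebo subjects given the same volumes can tell more drug from more vehicle. The design provides such subjects, and the summary tables then merge them into one column.

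For outcomes that do not depend on volume this is harmless. For cough, throat irritation or dyspnea after an inhaled liposome solution it might not be. Section 1.3 names respiratory toxicity as the one additional risk suspected for the liposomal product. If irritation rose with volume, high doses would look worse against pooled placebo than against matched placebo, and low doses better. A vehicle effect could then pass for a dose response in a trial whose primary objective is tolerability, and the stated purpose of the placebo would be weakened.

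**Working it through.** **Inputs from the protocol.** 8 groups of 8, allocated 6:2; loaded doses of 60 to 480 µg in steps of 60 (Table 2); concentration 1.5 mg/mL (Table 2 footnote).

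**Reproducing the plan's figures.**
- Subjects: 8 × (6 + 2) = 64, of whom 8 × 2 = 16 receive placebo and 48 receive L606. The sentinel groups give (1 + 5):(1 + 1) = 6:2, the same ratio.
- Volume = loaded dose / 1.5 mg/mL = 40, 80, …, 320 µL. This agrees with every row of Table 2.
- Mean volume in the placebo pool = 180 µL. The groups differ from it by −140, −100, −60, −20, +20, +60, +100 and +140 µL.

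**Offset caused by pooling.** Let E be a linear vehicle effect over 40 to 320 µL, in between-subject SDs. The protocol gives no value for E, so a range is assumed. The offset in group k against pooled placebo is E × (volume − 180)/280.

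| Assumed E (SD) | Group 8 | Group 1 | Groups 5 / 4 |
|---|---|---|---|
| 0 | 0 | 0 | 0 |
| 0.25 | +0.13 | −0.13 | ±0.02 |
| 0.5 | +0.25 | −0.25 | ±0.04 |
| 1.0 | +0.50 | −0.50 | ±0.07 |

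**What pooling gains in precision.**
- Against 16 pooled placebo subjects: SE = √(1/6 + 1/16) = 0.479 SD.
- Against the group's own 2: SE = √(1/6 + 1/2) = 0.816 SD. The variance is 2.9 times as large.
- With no events seen, the one-sided 95% upper bound on the placebo rate is 1 − 0.05^(1/16) = 17% for 16 subjects and 1 − 0.05^(1/2) = 78% for 2.
- For Groups 1 and 8, matched placebo has the smaller mean squared error only if 0.5E exceeds √(1/2 − 1/16) = 0.661, that is, if E is above about 1.3 SD.

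**A middle course: placebo from Groups 1–4 and 5–8 separately (8 each).** Suppose the vehicle-related event rate is k·r in group k, with r the rise per 40 µL and no drug effect. Pooled placebo then expects 4.5r, and the halves expect 2.5r and 6.5r. Error of the dose-level comparison:

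| Group | Against pooled placebo | Against its half |
|---|---|---|
| 1 | −3.5r | −1.5r |
| 4 | −0.5r | +1.5r |
| 5 | +0.5r | −1.5r |
| 8 | +3.5r | +1.5r |

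The split helps at the extremes and triples the bias in Groups 4 and 5. It also creates a false drop of 3r between those two neighbouring groups: 6 points at r = 2 and 15 points at r = 5.

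For Group 8, where the split does best, the root mean squared error of the placebo reference is √(bias² + Σp(1−p)/n²), summed over the n placebo subjects used:
- r = 2 points: pooled √(7² + 7.1²) = 9.9; split √(3² + 11.9²) = 12.2. The split is worse.
- r = 5 points: pooled √(17.5² + 10.0²) = 20.2; split √(7.5² + 16.4²) = 18.1. The split is slightly better.

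These values of r are assumptions. They imply vehicle-only event rates in Group 8 of 8 × 2 = 16% to 8 × 5 = 40%, which no passage supports.

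**The case for a change.** The strongest opposing case is that the protocol itself fixes pooling, in two places, so this is not a matter left open for the SAP. Readers judge dose response from summary tables whether or not a test is attached, and listings preserve the data without summarizing them by volume. The 1.3 SD break-even concerns 2 matched subjects. For halves of 8 it is lower: in Groups 1 and 8, equating 1/16 + (0.5E)² with 1/8 + (1.5E/7)² gives E of about 0.55 SD, and averaged over all eight groups it is 0.875 SD. A split shown beside the pooled column would cost little.

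Much of this stands. The offset would be real if the vehicle effect were real, and a display of placebo respiratory events by group would do no harm. It does not establish a fault, for four reasons:

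- Drug and volume are collinear because the concentration is fixed, not because placebo is pooled. The matched placebo subjects remain in the design and in the listings.
- Even the lower break-even needs a vehicle effect of half an SD or more, and the protocol reports none. Section 1.3 offers only a speculation about respiratory toxicity.
- Spirometry and oxygen saturation are not among the endpoints in Section 2.2.1, and their first postdose measurement is on Day 2 (Appendix 5). They would capture an acute volume effect poorly, which leaves mainly respiratory adverse events.
- The protocol prescribes no formal contrast of each dose with pooled placebo, and it does not rule out further displays.

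**Conclusion.** The concern does not hold. The volume matching, the 40 to 320 µL range, the 16 planned placebo subjects and the pooling are all as described, but none is an error or a contradiction. The Synopsis and Section 8.4 agree, the summaries are descriptive, and neither escalation nor stopping depends on the pooled column.

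The possible distortion is zero without a vehicle-volume effect. Under an assumed linear effect of 0.25 to 1.0 SD over the whole range, it is 0.13 to 0.50 SD in the two extreme groups and at most 0.07 SD in Groups 4 and 5. Against that, pooling lowers the standard error from 0.82 to 0.48 SD compared with matched pairs. A two-way split removes bias at the extremes, adds it in the middle, and is not reliably more accurate even for Group 8. The choice is a trade-off of bias against precision, and pooling is a reasonable side to take with 2 placebo subjects per group.

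These figures rest on the planned eight groups. The three optional groups in Section 3.3 would add up to 3 × 2 = 6 placebo subjects, for a total of 22. The effect sizes are assumptions, because the protocol gives none.

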#### **Pharmacokinetics:**

Plasma concentrations and PK parameters of treprostinil will be listed and summarized using descriptive statistics (arithmetic mean, standard deviation, minimum, median, and maximum, geometric mean, and geometric coefficient of variation, as appropriate). Individual and mean treprostinil concentration-time profiles will also be presented graphically.

The AUCs and  $C_{max}$  will be the primary endpoints for the evaluation of dose proportionality. Dose proportionality of treprostinil will be evaluated by assessing the slope from regression analysis of log(AUC or  $C_{max}$ ) versus log(dose) from the power model for those subjects who receive L606.

## LIST OF ABBREVIATIONS

Abbreviation	Definition
AE	adverse event
ALT	alanine aminotransferase
API	active pharmaceutical ingredient
AST	aspartate aminotransferase
AUC	area under the plasma concentration-time curve
$AUC_{0-\infty}$	area under the plasma concentration-time curve from time zero to infinity
AUC 0-tlast	area under the plasma concentration-time curve from time zero to the time of the last quantifiable concentration
AUC 0-2hr	area under the plasma concentration-time curve from time zero to 2 hours postdose
AUC 0-4hr	area under the plasma concentration-time curve from time zero to 4 hours postdose
AUC 0-8hr	area under the plasma concentration-time curve from time zero to 8 hours postdose
AUC 0-12hr	area under the plasma concentration-time curve from time zero to 12 hours postdose
AUC 0-24hr	area under the plasma concentration-time curve from time zero to 24 hours postdose
BA	bioavailability
CFR	Code of Federal Regulations
CL/F	apparent total plasma clearance
C max	maximum observed plasma concentration
COPD	chronic obstructive pulmonary disease
CRO	Contract Research Organization
CRU	Clinical Research Unit
CSA	clinical study agreement
EDC	electronic data capture
ECG	electrocardiogram
eCRF	electronic Case Report Form
FDA	Food and Drug Administration
FEV1	forced expiratory volume in 1 second
FVC	forced vital capacity
GCP	Good Clinical Practice
GLP	Good Laboratory Practice

HED	human equivalent dose
ICF	Informed Consent Form
ICH	International Council for/Conference on Harmonisation
IMP	investigational medicinal product
IRB	Institutional Review Board
IUD	intrauterine device
IV	intravenous
L606	Liposomal Treprostinil Inhalation Solution
MPC	mouthpiece cartridge
MTD	maximum tolerated dose
NOAEL	no observed adverse effect level
PAH	pulmonary arterial hypertension
PBI	Pharmosa Biopharm Inc
РК	pharmacokinetic(s)
QTcF	QT interval corrected for heart rate using Fridericia's method
SAE	serious adverse event
$t_{1/2}$	apparent plasma terminal elimination half-life
t max	time of the maximum observed plasma concentration
TMF	Trial Master File
ULN	upper limit of normal
$V_z/F$	apparent volume of distribution during terminal phase

## 1. INTRODUCTION

## 1.1. Overview

Pharmosa Biopharm Inc (PBI) is developing L606 (Liposomal Treprostinil Inhalation Solution) (hereafter called L606), a new liposomal treprostinil formulation for inhalation use in the treatment of patients with World Health Organization (WHO) Group I pulmonary arterial hypertension (PAH) and New York Heart Association (NYHA) Class III symptoms, to increase exercise ability.

L606 is planned to be administered via the same inhaled route as Tyvaso®, which is USA Food and Drug Administration (FDA) approved for the indication of PAH in patients. L606 is composed of liposomes (>100 nm) in sodium citrate-bicarbonate buffer. The liposomes are composed of hydrogenated soybean phosphatidyl choline (HSPC), cholesterol, and sodium distearoyl phosphatidyl glycerol (DSPG-Na).

Liposomes as a pulmonary drug delivery system have been reported to enhance the therapeutic benefits of drugs and to reduce the potential for systemic adverse effects. Studies have established the high biocompatibility and biodegradability of liposomes as drug carriers in inhaled formulations.

The L606 solution uses PBI's proprietary liposomal formulation to encapsulate the treprostinil, which can be released slowly under a controlled manner/rate into the lung. This control enables modulation of drug release to achieve optimized drug exposure over an extended period of time and reducing local irritation on the respiratory tract. The L606 inhalation system consists of a mesh-vibrating nebulizer that has been approved for use in Europe.

### 1.2. Inhaled Treprostinil Background

## **1.2.1.** General Pharmacology

Treprostinil, 2-[[(1R,2R,3aS,9aS)-[[2,3,3a,4,9,9a-hexahydro-2-hydroxy-1-[(3S)-3hydroxyoctyl]-1Hbenz[f]inden-5-yl]oxy]acetic acid, is a chemically stable tricyclic analogue of prostacyclin, a strong vasodilator and potent inhibitor of platelet aggregation. The pharmacology of treprostinil is well-characterized and approved for the treatment of PAH following either the subcutaneous, intravenous (IV), inhaled (as treprostinil sodium), or oral (as treprostinil diolamine) routes of administration.

Treprostinil for inhalation (Tyvaso) is approved in the United States for the treatment of PAH (World Health Organization Group I) in patients with New York Heart Association functional classification III symptoms, to increase exercise ability.

Tyvaso was developed for oral inhalation using the Tyvaso inhalation system, an ultrasonic, pulsed-delivery device.

# **1.2.2.** General Toxicology

A well-defined clinical safety profile exists for treprostinil sodium; acute toxicity studies and repeat-dose toxicity studies performed in both rats and dogs, and reproductive toxicity and genotoxicity studies support the chronic administration to patients.

In addition, a 2-year rat carcinogenicity study was performed with treprostinil inhalation at target doses up to 5.26, 10.6, and 34.1  $\mu$ g/kg/day which found no evidence for carcinogenic potential associated with inhaled treprostinil in rats at systemic exposure levels up to 35 times the clinical exposure at the target maintenance dose of 54  $\mu$ g.

## **1.2.3.** Clinical Experience

Pilot clinical studies have elucidated the acute hemodynamic effects and relative pulmonary selectivity of Tyvaso, and have demonstrated clinical and hemodynamic improvement with chronically administered Tyvaso. Both pilot studies confirmed a satisfactory safety profile in patients with PAH. The pivotal Phase 3 trial, TRIUMPH-I, demonstrated the efficacy and safety of Tyvaso (target dose of 54  $\mu$ g four times daily) added to background therapies of bosentan or sildenafil in PAH patients, as assessed by improvements in exercise ability.

The effects of Tyvaso diminish over the minimum recommended dosing interval of 4 hours. Overall, in clinical studies the most common adverse reactions ( $\geq 10\%$ ) to Tyvaso were cough, headache, nausea, dizziness, flushing, throat irritation, pharyngolaryngeal pain, and diarrhea.

